9.3.2 Analysis of Secondary Efficacy Variables

Absolute change in sweat chloride from baseline at Week 8

A similar MMRM model will be used for the above variable using the same approach as described for the analysis of the primary efficacy variable, with the addition of baseline sweat chloride as a covariate. The assessment of efficacy will be primarily based on the estimated mean change from baseline at Week 8.

Similar summary tables will also be provided using the same approach as described for the analysis of the primary efficacy variable.

Absolute change in the CFQ-R respiratory domain score from baseline through Week 8

A similar MMRM model will be used for the CFQ-R respiratory domain score based on the children's version, using the same approach as described for the analysis of the primary efficacy variable, with the addition of baseline CFQ-R respiratory score as a covariate.

Summary tables will also be provided for both the children's version and the parents/caregivers' version using the same approach as described for the analysis of the primary efficacy variable.

9.4 Safety Analysis

All safety analyses will be based on the Safety Set. Subjects will be analyzed according to the treatment they actually received. Only descriptive analysis of safety will be performed (i.e., no statistical hypothesis testing will be performed). The safety endpoints will be summarized using descriptive summary statistics by treatment group and overall. Due to the small sample size, the summary on F/RF subjects treated with IVA and F/F subjects treated with placebo should be interpreted with caution.

The overall safety profile of study drug will be assessed in terms of the following safety and tolerability endpoints:

- Treatment-emergent adverse events (TEAEs)
- Clinical laboratory values
- Standard 12-lead ECGs
- Vital signs
- Pulse oximetry
- Ophthalmologic examination
- Serial lung function (post-dose spirometry)

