**Secondary Endpoints**

- Absolute change from baseline in sweat chloride at Week 8
- Absolute change in Cystic Fibrosis Questionnaire-Revised (CFQ-R) respiratory domain score from baseline through Week 8
- Safety and tolerability as measured by adverse events (AEs), clinically significant changes in laboratory values (serum chemistry, hematology, coagulation studies, lipids, vitamin levels, and urinalysis), standard 12-lead ECGs, vital signs, pulse oximetry, serial lung function measurement, and ophthalmologic examinations.

Number of Subjects	Approximately 65 subjects total, of which up to 15 subjects are heterozygous for F508del and a second CFTR allele that results in residual function (F/RF)
Study Population	Male and female subjects aged 6 through 11 years with CF who are F/F or F/RF
Investigational Drug	
Active substance: TEZ and IVA
 
Activity: CFTR corrector and potentiator (increased Cl secretion)
 
Strength and route of administration: TEZ 50 mg/IVA 75 mg fixed-dose combination (FDC) tablet or TEZ 100 mg/IVA 150 mg FDC tablet; oral administration
 
Active substance: IVA
 
Activity: CFTR potentiator (increased Cl secretion)
 
Strength and route of administration: IVA 75- or 150-mg tablet; oral administration
 
Active substance: Not applicable
 
Activity: Placebo
 
Strength and route of administration: 0-mg matching placebo tablets for oral administration

Study Duration	Each subject will participate in the study for 16 weeks: 4-week Screening Period, 8-week Treatment Period, and 4-week Safety Follow-up Period.

[figure not shown]

**Study Design** This is a Phase 3, double-blind, parallel-group study in subjects with CF who are homozygous or heterozygous for the *F508del-CFTR* mutation. The study is designed to evaluate the efficacy and safety of TEZ/IVA treatment in pediatric subjects aged 6 through 11 years.

[figure not shown]
Subjects will be stratified by genotype group (F/F or F/RF) and randomized 4:1 (TEZ/IVA: blinding arm) and treated as shown in Figure 2-1. The blinding arm will be placebo for F/F subjects and IVA monotherapy (with TEZ-matching placebo) for F/RF subjects.

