### 12.3 Statistical Analysis

The Vertex Biometrics Department or designee will analyze the safety and efficacy data.

The primary objective of this study is efficacy. The secondary objective is safety. This section summarizes the statistical analysis of efficacy and safety data. Methodological and related details (e.g., missing data) will be provided in the SAP.

The primary efficacy endpoint is the absolute change in  $LCI_{2.5}$  from baseline through Week 8. The objective of primary efficacy endpoint analysis is to demonstrate that the mean absolute change from baseline in  $LCI_{2.5}$  through Week 8 for subjects on TEZ/IVA excludes a pre-defined maximum placebo effect. The primary analysis of the primary efficacy endpoint will be based on a mixed-effects model for repeated measures (MMRM) with  $LCI_{2.5}$  at each time point as the outcome variable. The estimated mean change from baseline through Week 8 in  $LCI_{2.5}$  for subjects on TEZ/IVA along with the corresponding 95% CI will be provided. If the upper bound of the 95% CI is below the pre-defined maximum possible placebo effect, it will be interpreted as sufficient evidence to achieve the primary efficacy objective.

The study plans to enroll approximately 50 F/F subjects and up to 15 F/RF subjects.

A placebo group of F/F subjects and an IVA mono group of F/RF subjects will be included in this study. The main purpose is to preserve blinding, so that subjects and investigators do not assume a subject is receiving TEZ/IVA, which could introduce bias into the results. Descriptive statistics such as mean and SD will be provided for change from baseline in  $LCI_{2.5}$  at each post-baseline visit for homozygous subjects in the placebo group.

The target enrollment by genotype and treatment group is provided in the Table 12-1.

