#### 12.3.4.1 Adverse Events

AEs will be classified as pretreatment AEs or treatment-emergent AEs (TEAEs), defined as follows:

**Pretreatment AE:** any AE that started before the first dose date of study drug

**TEAE:** any AE that worsened (either in severity or seriousness) or that was newly developed at or after the first dose date of study drug through the end of the TE period

For AEs with completely missing or partially missing start dates, if there is no clear evidence that the AEs started before or after study treatment, the AEs will be classified as TEAEs.

Details for imputing missing or partial start dates of AEs are described in the SAP.

AE summary tables will be presented for TEAEs only, overall and by treatment group, and will include the following:

- All TEAEs
- TEAEs by strongest relationship
- TEAEs by maximum severity
- TEAEs leading to treatment discontinuation
- Serious TEAEs
- TEAEs leading to death

Summaries will be presented by MedDRA SOC and PT using frequency counts and percentages (i.e., number and percentage of subjects with an event). When summarizing the number and percentage of subjects with an event, subjects with multiple occurrences of the same AE or a continuing AE will be counted once. Only the maximum severity level will be presented in the severity summaries, and the strongest relationship level will be presented in the relationship summaries.

In addition, a listing containing individual subject AE data for TEAEs leading to treatment discontinuation, SAEs, and deaths will be provided separately. All AEs, including pretreatment AEs, will be presented in an individual subject data listing.

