7 STUDY DESIGN

7.1 Overall Design

[figure not shown]
This is a Phase 3, double-blind, parallel-group study in subjects with CF aged 6 to 11 years, homozygous or heterozygous for *F508del*. Subjects will be:

- homozygous for *F508del* (F/F), or
- heterozygous for *F508del* and a second allele with a residual function mutation (F/RF).

A schematic of the study design is shown in Figure 6-1.

Figure 7-1 VX16-661-115 Study Design

Notes: Subjects who are taking commercially available CFTR modulators (Orkambi or Kalydeco) are required to washout for 28 days before the Day 1 Visit. The study will enroll a total of approximately 65 subjects, of which up to 15 subjects have an F/RF genotype. Subjects will be stratified by genotype group (F/F or F/RF) and randomized 4:1 (TEZ/IVA: blinding arm) before receiving the first dose of study drug on Day 1. The blinding treatment arm will be placebo for F/F subjects and IVA monotherapy (with TEZ-matching placebo) for F/RF subjects. Study drug dose is determined based on weight on Day 1 (<40 kg or ≥40 kg). Subjects will receive matched TEZ/IVA placebo or IVA placebo tablets as appropriate. See Table 9-2 for additional information on study drug tablets and dosing.

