7.3 Randomization

Approximately 65 subjects, of which up to 15 subjects have F/RF genotypes, will be stratified by genotype and randomized 4:1 to study drug treatment.

An interactive web or voice response system (IXRS) will be used to assign subjects to treatment. Detailed instructions for randomization will be provided separately.

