9.3.1 Analysis of the Primary Efficacy Variable

The primary efficacy endpoint is the absolute change in $LCI_{2.5}$ from baseline through Week 8. The objective of the primary efficacy endpoint analysis is to demonstrate that the mean absolute change from baseline in $LCI_{2.5}$ through Week 8 excludes a pre-defined maximum placebo effect in subjects in the TEZ/IVA group.

The primary analysis will be performed using a restricted maximum likelihood (REML)-based mixed-effect model for repeated measures (MMRM) for the subjects in the TEZ/IVA treatment group in the FAS population. The model will include absolute change from baseline in $LCI_{2.5}$ (including all measurements up to Week 8 [inclusive], both on treatment measurements and measurements after treatment discontinuation) as the dependent variable, and visit (as a class variable) as a fixed effect, with adjustment for mutation group based on the second *CFTR* allele (F/F and F/RF) and baseline $LCI_{2.5}$ (continuous) value as covariates, and subject as a random effect. An unconstructed covariance structure will be used to model the within-subject errors. If the model fails to converge, a compound symmetry covariance structure will be considered. The degrees of freedom of the denominator will be approximated by the Kenward-Roger's method².

The primary results obtained from the model will be the estimated average treatment effect through Week 8 in $LCI_{2.5}$ for subjects on TEZ/IVA. The corresponding LS mean, standard error (SE), 95% CI, and *p*-value will be provided. If the upper bound of the 95% CI is below the pre-defined maximum possible placebo effect, which was specified in the protocol, it will be considered that the study has achieved its primary objective. Summary statistics for change from baseline in $LCI_{2.5}$ through Week 8, and at each visit will also be provided for subjects in the TEZ/IVA treatment group by mutation groups and overall.

For F/F subjects in the placebo treatment group, summary statistics will be provided for change from baseline in LCI_{2.5} through Week 8, and at each visit.

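### On the natural reading, the safety tables pool both genotypes on TEZ/IVA beside single-genotype control columns, so the descriptive columns are not like-for-like (minor)

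*SAP*

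**What the plan says.** SAP 7.3 says subjects "will be stratified by genotype and randomized 4:1 to study drug treatment", and SAP 7.1 gives each stratum its own control: "The blinding treatment arm will be placebo for F/F subjects and IVA monotherapy (with TEZ-matching placebo) for F/RF subjects". Protocol 12.3 describes the controls in the same way: "A placebo group of F/F subjects and an IVA mono group of F/RF subjects will be included in this study". It adds that their main purpose is to protect the blind. Protocol Table 12-1 sets the targets at 40 TEZ/IVA and 10 placebo in F/F, and 12 TEZ/IVA and 3 IVA in F/RF.

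For safety, SAP 9.4 says: "The safety endpoints will be summarized using descriptive summary statistics by treatment group and overall". Protocol 12.3.4.1 has the same layout: "AE summary tables will be presented for TEAEs only, overall and by treatment group". Neither SAP 9.4.1 to 9.4.8 nor Protocol 12.3.4 requests a genotype split. SAP 9.4 advises caution about the IVA and placebo summaries because those groups are small. It does not mention the genotype mix of the TEZ/IVA column.

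For LCI, by contrast, SAP 9.3.1 asks for summaries in the "TEZ/IVA treatment group by mutation groups and overall". When the SAP wants a split it says so, and it treats TEZ/IVA as one group holding both genotypes.

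**The concern.** The design contains two small randomised comparisons with different controls. If the safety tables carry one TEZ/IVA column, that column mixes both genotypes while each control column holds one. Any difference between F/F and F/RF children in event incidence or raw level would then contribute to the visible gap between columns, even if the drug did nothing.

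A genotype difference is plausible from the documents, though they do not quantify one. Under Protocol 8.1 (criterion 6), F/RF children may enter with sweat chloride below 60 mmol/L if they have other documented evidence of disease; F/F children may not. Protocol 9.1.4 and 10.7 also allow discontinuation of a genotype subset, with the risks and benefits seen in that subset communicated to investigators and ethics boards. Safety is the secondary objective, so a clear display by stratum has some value.

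**Working it through.** **Inputs.** Protocol 12.3: "The study plans to enroll approximately 50 F/F subjects and up to 15 F/RF subjects". Allocation is 4:1 within genotype (SAP 7.1). The documents give no safety precision or power figure, so the plan's figure to reproduce is Table 12-1.

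**Step 1. Reproduce Table 12-1.**
- F/F: 50 × 4/5 = 40 and 50 × 1/5 = 10.
- F/RF: 15 × 4/5 = 12 and 15 × 1/5 = 3.

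Both match.

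**Step 2. Genotype mix of each column, if TEZ/IVA is pooled.**

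| Column | n | F/F | F/RF |
|---|---|---|---|
| TEZ/IVA | 52 | 40 (77%) | 12 (23%) |
| Placebo | 10 | 10 (100%) | 0 |
| IVA | 3 | 0 | 3 (100%) |
| Overall | 65 | 50 (77%) | 15 (23%) |

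No two treatment columns share a mix.

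**Step 3. Apparent difference with no drug effect.** Let p_F and p_R be the incidences in F/F and F/RF, and D = |p_F − p_R|.
- Pooled TEZ/IVA rate = (40 p_F + 12 p_R)/52.
- Against placebo: pooled − p_F = (12/52)(p_R − p_F), of size 0.231 D.
- Against IVA: pooled − p_R = (40/52)(p_F − p_R), of size 0.769 D.

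**Step 4. Range over D (assumed).**

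| D (points) | vs placebo (points) | vs IVA (points) |
|---|---|---|
| 0 | 0 | 0 |
| 10 | 2.3 | 7.7 |
| 20 | 4.6 | 15.4 |
| 30 | 6.9 | 23.1 |
| 40 | 9.2 | 30.8 |

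For example, 80% in F/F and 50% in F/RF give a pooled rate of (32 + 6)/52 = 73.1%, which is 6.9 points below placebo and 23.1 above IVA.

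**Step 5. Compare with one child.** One child is 1/10 = 10 points on placebo and 1/3 = 33.3 points on IVA. The artefact reaches one child only at D = 10/0.231 = 43 points against placebo, and at D = 33.3/0.769 = 43 points against IVA.

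**Step 6. Compare with sampling error, at an assumed 50% incidence.** The standard error of a difference is √(0.25/n₁ + 0.25/n₂).
- Pooled: 52 vs 10 gives 17 points; 52 vs 3 gives 30 points.
- Split: 40 vs 10 gives 18 points; 12 vs 3 gives 32 points.

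**Step 7. After splitting.** Each comparison is within a randomised stratum, so the genotype-mix term is zero. Precision stays poor. With no events, the one-sided 95% upper limit, 1 − 0.05^(1/n), is 7.2% (n = 40), 25.9% (n = 10), 22.1% (n = 12) and 63.2% (n = 3).

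**The case against.** The strongest case on the other side is that nothing planned depends on these comparisons. Safety is descriptive with no testing, the controls exist mainly for blinding, and the primary analysis uses the TEZ/IVA group alone. The safety objective covers both genotypes, so the pooled TEZ/IVA column answers it directly. SAP 9.2.2 tabulates mutation by treatment group, and the SAP 9.4 caution already names each control group's genotype. Individual listings are also provided. The artefact is smaller than one child over the range considered, and a column of 3 cannot support a comparison however the table is laid out.

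Most of this stands, and it sets the severity. It does not remove the mismatch. Side-by-side columns invite comparison, the stated caution concerns size only, and a baseline table of genotype does not supply event rates within genotype.

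A reader might infer three stronger points, which the documents do not support:
- *That a planned safety contrast is confounded.* No difference, ratio or test between arms is specified for safety. The pooled column is also a reading of SAP 9.4, not an explicit statement.
- *That laboratory and lung-function results in general are distorted.* Many of these summaries are changes from baseline, or from the same-day predose value, in which stable level differences between genotypes cancel. The exposure is in incidences, threshold events, raw values and any genotype-specific change.
- *That the overall column, with its 13 control children, will be reported as the TEZ/IVA rate.* Nothing says so; TEZ/IVA is summarised separately.

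**Conclusion.** The point holds as a cheap improvement of minor severity. On the natural reading of SAP 9.4, the TEZ/IVA safety column is 23% F/RF, while placebo is all F/F and IVA all F/RF. The columns therefore differ in genotype mix as well as drug. The artefact is 0.23 × D against placebo and 0.77 × D against IVA: 0 to 9 and 0 to 31 points for D between 0 and 40.

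This rests on the Table 12-1 targets being met, on TEZ/IVA being pooled, and on a value of D that the documents do not give and that may be zero. F/RF enrolment is a maximum. With 10 F/RF children instead of 15 and F/F held at 50, the F/RF share of TEZ/IVA would be 8/48 = 17%, and the factors would be 0.17 and 0.83. The primary analysis and the power calculation are unaffected.

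**What to change.** In SAP 9.4, define the columns for the main TEAE tables and for the threshold-event and raw-value summaries:
- F/F TEZ/IVA beside F/F placebo;
- F/RF TEZ/IVA beside F/RF IVA;
- all TEZ/IVA, kept as the main safety summary for the stated objective.

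Extend the existing small-sample caution with a sentence saying that the pooled TEZ/IVA and overall columns differ from each control column in genotype mix. If a split is already intended, one sentence in SAP 9.4 saying so is enough.

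The cost is SAP wording, table shells and wider tables; data collection does not change. The gain is a like-for-like F/F display of 40 against 10. The F/RF columns, 12 against 3, will remain too small to interpret.

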9.4.1 Adverse Events

AEs will be coded according to MedDRA and classified as pretreatment AEs, TEAEs, or post-treatment AEs, defined as follows:

Pretreatment AE: any AE that started before the first dose date of study drug.

TEAE: any AE that worsened (either in severity or seriousness) or that was newly developed at or after the first dose date of study drug through the end of the TE period.

Post-treatment AE: any AE that worsened (either in severity or seriousness) or that was newly developed beyond the TE period.

For AEs with completely missing or partially missing start dates, if there is no clear evidence that the AEs started before or after study treatment, the AEs will be classified as TEAEs.

Details for imputing missing or partial AE start/end dates are defined in [Appendix E](#).

9.4.1.1 Overview of TEAEs

An overview table of TEAEs will be provided with the following categories:

- Number of TEAEs (total number of TEAEs)
- Subjects with any TEAEs
- Subjects with TEAEs by strongest relationship
- Subjects with TEAEs by maximum severity
- Subjects with related TEAEs
- Subjects with Grade 3/4 TEAEs
- Subjects with serious TEAEs
- Subjects with related serious TEAEs
- Subjects with TEAEs leading to treatment discontinuation
- Subjects with TEAEs leading to treatment interruption
- Subjects with TEAEs leading to death

In addition, a listing containing individual subject adverse event data for TEAEs leading to treatment discontinuation, treatment interruptions, SAEs and all deaths will be provided separately, with a flag indicating the TEAE status for SAEs and deaths.

For all AEs, the action taken on the CRF for TEZ/IVA (AM dose) is collected separately from the AE action taken for IVA (PM dose). As a result, it is possible that in the AE dataset, the AE actions taken for the two agents are different. The summaries of TEAEs Leading to Treatment Discontinuation or Interruptions account for discontinuation and interruptions for either agent.

9.4.1.2 TEAEs by SOC and PT

In addition, the following summary tables of TEAEs will be provided:

- All TEAEs
- Related TEAEs
- Grade 3/4 TEAEs
- Serious TEAEs
- Related serious TEAEs
- TEAEs leading to treatment discontinuation
- TEAEs leading to treatment interruption
- TEAEs leading to death

Summaries will be presented by MedDRA SOC and PT using frequency counts and percentages (i.e., number and percentage of subjects with an event). When summarizing the number and percentage of subjects with an event, subjects with multiple occurrences of the same AE or a continuing AE will be counted once. Only the maximum severity level will be

presented in the severity summaries, and the strongest relationship level will be presented in the relationship summaries.

9.4.1.3 TEAEs and SAEs by PT

The number and percentage of subjects with TEAEs and SAEs will be summarized by PT, where multiple occurrences of the same adverse event or a continuing adverse event for the same subject will be counted once.

9.4.1.4 Respiratory Events and Symptoms

Respiratory symptoms are defined as any TEAEs for the following 3 PTs:

- Chest discomfort
- Dyspnoea
- Respiration abnormal

Respiratory events are defined as any of the afore-mentioned respiratory symptoms, or any TEAEs for the following 4 additional PTs:

- Asthma
- Bronchial hyperreactivity
- Bronchospasm
- Wheezing

Summary tables of respiratory symptoms and events will be provided by PT.

9.4.1.5 Elevated Transaminase

The following AE preferred terms will be selected for elevated transaminase:

- Alanine aminotransferase abnormal
- Alanine aminotransferase increased
- Aspartate aminotransferase abnormal
- Aspartate aminotransferase increased
- Transaminases abnormal
- Transaminases increased
- Liver function test abnormal
- Liver function test increased
- Hypertransaminasaemia
- Hepatic enzyme abnormal
- Hepatic enzyme increased

A summary table will be provided for elevated transaminases events by PT.

9.4.2 Clinical Laboratory

For treatment-emergent laboratory measurements, the raw values and change from baseline values of the continuous hematology, chemistry, vitamin, lipids and coagulation results will be summarized in SI units at each scheduled time point.

The number and percentage of subjects with events meeting threshold criteria laboratory event during the TE period will be summarized by treatment group and overall. The threshold analysis criterion shift from baseline will also be summarized for selected laboratory parameters. The threshold criteria are provided in [Appendix G](#).

Results of urinalysis and the urine/serum pregnancy test will be listed in individual subject data listings only.

In addition, a listing of each subject's liver function test (LFT), non-LFT chemistry, hematology, vitamin, lipid, and coagulation results outside the reference ranges will be provided. This listing will include data from scheduled and unscheduled visits.

For liver function tests (LFTs) (i.e. alanine aminotransferase [ALT], aspartate aminotransferase [AST], alkaline phosphatase [ALP], and total bilirubin), the following additional analyses will be presented:

- A listing of subjects with elevated LFT results during the TE period will be presented. For each subject in the listing, LFT assessments at all the time points will be included (scheduled and unscheduled).
- Mean values (\pm SD) will be plotted by visit, and box plots of the LFT values/ULN will be plotted by visit.

Summary tables for the shift from baseline to the value at Week 8 will be provided for vitamin levels and the lipid panel. Box plots of vitamin levels and the lipid panel will also be plotted against visit.

